What is the effectiveness of MDFT on the frequency of self-reported substance use, measured at 6-months post-randomisation, for young people aged 13-17 years, who are current substance users and involved in criminal activity or considered at risk of becoming involved in criminal activity compared with business as usual.

Secondary research questions

What is the effectiveness of MDFT on the frequency of self-reported substance use, measured at 12-months post-randomisation, for young people aged 13-17 years, who are current substance users and involved in criminal activity or considered at risk of becoming involved in criminal activity compared with business as usual.

ERQ3 What is the effectiveness of MDFT on the frequency of violent offending at 6- and 12-months post randomisation compared with business as usual

- **ERQ4** What is the effectiveness of MDFT on behavioural and emotional difficulties at 6-and 12-months post randomisation compared to business as usual
- **ERQ5** What is the effectiveness of MDFT on mental health and wellbeing at 6- and 12-months post randomisation compared to business as usual
- ERQ6 What is the effectiveness of MDFT on substance use related problems at 6- and 12-months post randomisation compared to business as usual
- ERQ7 What is the effectiveness of MDFT on substance use related problems at 6- and 12-months post randomisation compared to business as usual
- **ERQ8** What is the effectiveness of MDFT on the frequency of criminal justice outcomes, arrests, cautions, charges and court attendance, at 6- and 12-months post randomisation compared to business as usual
- **ERQ9** What is the effectiveness of MDFT on the frequency of educational outcomes, suspensions, exclusions and managed moves, at 6- and 12-months post randomisation compared to business as usual
- ERQ10 What is the cost per participant associated with the delivery of MDFT
- **ERQ11** To develop a prognostic model exploring the baseline demographics, psychological and family factors that may impact observed outcomes and using the results to elaborate mechanisms of change and where appropriate revise the intervention logic model.
- **ERQ12** To conduct a latent class analysis to explore potential interactions between population subgroups, intervention received, and outcomes observed. Specific sub-groups include ethnicity, sex, age, offending behaviour and substance use severity.

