estimates found in systematic reviews of MDFT (Filges T. et al., 2018, van der Pol et al., 2017b). This equates to a number needed to treat of 6, where at least one in six participants receiving MDFT would show clinically important benefits, and a difference in the frequency of substance use of at least 13% in the MDFT group. Detecting an effect size smaller than this provides no additional benefit, the commissioning of services in England and Wales requires the service to achieve a clinically important difference for the target population. To detect this difference, with power at 80% and alpha of 0.05 and a two-tailed test, requires a sample of 480 participants followed-up at the 6-month endpoint. Using data from other studies of substance using adolescents (Coulton S et al., 2023, Deluca et al., 2020) we estimate the prepost-test correlation of the frequency of substance use to be 0.4, and incorporating this into the sample size calculation reduces the number followed-up to 364, 182 in each group. Assuming a loss to follow-up at the endpoint of 10%, similar to other studies in adolescent substance use populations (Coulton et al., 2024) inflates the number needed to randomise to 400. Assuming 80% of those eligible will be willing to consent an indication of acceptability of the study to participants and a lower figure than other studies in similar populations (Coulton et al., 2024) would mean we would need to approach 480 across both sites. Recruitment will be continuous between September 2025 and January 2027, 28 per month will need to be approached in total across both sites per month with the expectation that 24 will consent to participate in the trial across both sites. We anticipate. Based on relative population size that 40% of referrals will come from Newport and 60% from Bristol.

Table 2: Recruitment/ retention table

	Q1	Q2	Q3	Q4	Q5	Q6	Q7	Q8	Q9	Q10	Q11
Months (e.g. Oct-Dec 23):	May-Jul 25	Aug-Oct 25	Nov 25 - Jan 26	Feb - Apr 26	May-Jul 26	Aug-Oct 26	Nov 26 - Jan 27	Feb - Apr 27	May-Jul 27	Aug-Oct 27	Nov 27 - Jan 28
Target number of children and young people referred into the project	0	50	75	75	75	75	75	75	218	360	500
Target number of children and young people recruited to the project and evaluation	0	40	60	60	60	60	60	60	174	288	400
Target number of children and young people who withdraw/drop out	0	4	6	6	6	6	6	6	23	35	40

Table 3: Sample size calculations

		PARAMETER		
Minimum Detectable Effect Size (MDES)		0.27		

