Wellbeing will be assessed using the Short Warwick-Edinburgh Mental Well-being scale (SWEMWBS; (Clarke et al., 2011)). SWEMWBS is a 7-item, self-completed scale addressing different aspects of eudemonic and hedonic mental health wellbeing. The scale is validated for adolescents and demonstrates good internal consistency (Ng Fat et al., 2017), and discriminant, construct and convergent validity (McKay and Andretta, 2017, Ng Fat et al., 2017).

We will use questions derived from a Client Service Receipt Inventory (CSRI; (Coulton S et al., 2023) to assess school, work and criminal justice involvement over the previous 6-months. All these outcomes will be assessed at baseline and again at month 6.

To explore the mechanism of change we aim to assess changes in domains that are key targets of MDFT. The Brief Family relationship Scale (BFRS; (Fok et al., 2014)) will be used to assess family conflict and cohesion. Motivation to change will be assessed using the readiness to change ruler (RR; (Maisto et al., 2011)). Self-efficacy will be assessed using the short Situational Confidence Questionnaire (SCQ-8;(Breslin et al., 1998)). Positive and negative Expectancy will be assessed using a four-item expectancy measure (SUE; (Montes et al., 2019)).

Secondary outcomes will be assessed at baseline and at the 6-and 12-month follow-up points and have established psychometric properties in adolescent population. Therapeutic alliance will be assessed using the revised Therapeutic Alliance Scale for Children (TASC-r; (Shirk and Saiz, 1992)) at the 6-month follow-up only.

All outcome measures have been used previously in adolescent populations, and we estimate the outcome data set takes on between 10 and 20 minutes to complete.

Table 4: Core outcomes and the time of data collection.

Outcome	No of items	Baseline	Six months
Stratification			
Global Assessment of Individual Need – short screen (GAIN-SS)	5	✓	
Covariate			
Single Substance Use Question – 28 day (SUSQ28)	1	✓	
Primary			
Time Line Follow-Back – 28 (interview)			✓
Secondary			
Self-reported delinquency (SRDS) ¹	36	✓	✓
Strength and Difficulties (SDQ) ¹	25	✓	✓
Wellbeing (SWEBWMS)	7	✓	✓
Family cohesion and conflict (BFRS)	15	✓	✓
Alcohol and substance use problems (ESPAD)	8	✓	✓
Client Service Utilisation (CSRI)	8	✓	✓
Exploratory			
Motivation to change (RR)	1	✓	✓
Substance use expectancy (SUE)	4	✓	✓
Substance use efficacy (SCQ8)	8	✓	✓
Therapeutic Alliance (TASC-r)	12		✓

¹SRDS and SDQ are YEF core outcomes.

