Fractional regression analysis will be performed to model the relationship between prerandomisation factors, and demographics on observed outcomes at 6 months, for the primary outcome. Interaction terms with allocation arm will be included in the analysis, and a significance level of 0.1 will be used to determine which factors are to be included in the model. Pre-randomisation factors will include ethnicity, sex, age, IMD decile, severity of substance use, and baseline family cohesion, motivation, self-efficacy and expectancy. This analysis will be augmented by an additional analysis including participants in the intervention arm only using the same pre-randomisation factors but also including process measures of adherence, intervention fidelity, and therapeutic alliance.

Latent class approaches will be used to explore the hypothesised mechanism of change exploring changes over time in family cohesion, motivation to change, self-efficacy and substance use expectancy.

Qualitative analysis

The aim of the qualitative analysis in the efficacy study will be to link samples by grouping, comparing, and contrasting responses from all data sources to address the research questions. This linking of data allows for a concentrated and more meaningful analysis of the influence of the programme through its contexts and mechanisms, and of its perceived impact through a thematic blending of data elements. The key questions that we will seek to answer at this stage will include:

- Are there any residual or new external or logistical issues impacting referral, intervention delivery, or attrition?
- What are young peoples' positive and negative experiences of the intervention and how do these fit with providers' perceptions?
- At what points in the intervention have these experiences occurred?
- Are there practices associated with the intervention that can be amended to further increase its acceptability and impact?
- Do stakeholders see the intervention as impacting participant's behaviour?
- In what ways has substance use and offending been impacted?

This provides an opportunity to explore the perceptions of the intervention from the point of view of a variety of stakeholders using Normalisation Process theory (NPT; (Finch et al., 2012). Bracketing, reflexivity, and member checking will be employed to ensure trustworthiness and rigour.

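### Keeping factors and allocation interactions at p<0.1 in the exploratory model would select at least one false moderator in about 61% of null trials and drop most real ones of plausible size

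*Protocol*

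**What the plan says.** Under Exploratory analysis, the protocol states: "Fractional regression analysis will be performed to model the relationship between prerandomisation factors, and demographics on observed outcomes at 6 months, for the primary outcome". On effect modification it adds: "Interaction terms with allocation arm will be included in the analysis". The threshold for selection is then fixed: "a significance level of 0.1 will be used to determine which factors are to be included in the model". The candidate list is given there: "Pre-randomisation factors will include ethnicity, sex, age, IMD decile, severity of substance use, and baseline family cohesion, motivation, self-efficacy and expectancy". That is nine factors if expectancy is one score. The Secondary outcomes section leaves open whether it is one or two: "Positive and negative Expectancy will be assessed using a four-item expectancy measure".

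The section does not say whether interactions are fitted one at a time or jointly, whether the 0.1 level applies to interactions, main effects or both, or whether any allowance is made for the number of tests.

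ERQ11, under Secondary research questions, gives the purpose: a prognostic model, "using the results to elaborate mechanisms of change and where appropriate revise the intervention logic model".

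**The concern.** The protocol itself fixes a p-value selection rule here, so this is not a detail left to a statistical analysis plan. A lenient threshold applied to nine candidates can be expected to let false moderators through. Leniency is usually defended as protecting power for interactions, but at this sample size the power may still be poor.

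If both are true, a retained factor carries little evidence and its estimate is inflated by having been selected, while a dropped factor is uninformative. This matters most for ethnicity and sex: the Diversity, equity and inclusion section promises quantitative work on the role of ethnicity and disadvantage in outcomes, and ERQ11 draws on this model when mechanisms and the logic model are considered.

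**Working it through.** The protocol states no error rate or power for this step, so there is no figure of its own to reproduce. The sample size that the check relies on does reproduce: with d = 0.27, r = 0.4, two-sided 0.05 and 80% power, n per group = 2 × (1.96 + 0.842)² × (1 − 0.16) / 0.27² ≈ 181, or 362 in total, against the stated plan, which "reduces the number followed-up to 364, 182 in each group".

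**Inputs**
- Selection level 0.10 and nine factors: Exploratory analysis.
- n = 364, r = 0.40, effect 0.27 SD: Sample size calculations and Table 3.
- 35% racially minoritised and 35% female: Participants.
- Assumptions not in the protocol: independence of the nine tests (relaxed below), the 0.1 level applied to the interactions, and each factor as one parameter.

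**False selection when nothing moderates the effect**
- P(at least one of nine) = 1 − 0.9^9 = 0.613.
- Expected number of false selections = 9 × 0.1 = 0.9 per trial.
- With positive and negative expectancy as two scores: 1 − 0.9^10 = 0.651.

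**Relaxing independence.** Fractional logit models with robust standard errors were fitted to simulated 28-day outcomes with no true interaction (1,500 trials per setting). The probability of at least one interaction with p<0.1 was:

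| n | Latent correlation between factors | One at a time | All jointly |
|---|---|---|---|
| 364 | 0 | 64% | 66% |
| 364 | 0.3 | 61% | 65% |
| 364 | 0.5 | 51% | 62% |
| 400 | 0 | 64% | 65% |
| 400 | 0.3 | 62% | 67% |
| 400 | 0.5 | 53% | 63% |

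Monte Carlo error is about √(0.61 × 0.39 / 1500) = 1.3 percentage points. In the one-at-a-time fits, the per-test rate was 0.103–0.111 rather than exactly 0.10, which helps explain why some entries exceed 61%. Every setting is above one half.

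**Missed moderators.** For a binary factor with prevalence p, equal arms and baseline adjustment, the interaction (a difference between two treatment effects, in SD units) has SE = 2√(1 − r²) / √(n p (1 − p)).
- p = 0.35: SE = 2 × √0.84 / √(364 × 0.35 × 0.65) = 1.833 / 9.10 = 0.201. For a true 0.27 SD interaction, z = 0.27 / 0.201 = 1.34. Power at two-sided 0.10 ≈ Φ(1.34 − 1.645) ≈ 0.38, so it is dropped about 62% of the time.
- p = 0.50: SE = 1.833 / √91 = 0.192, power ≈ 0.41, dropped about 59% of the time.

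**Inflation by selection.** To be kept at 0.10 with p = 0.35, an estimate must exceed 1.645 × 0.201 = 0.33 SD in size. Every retained estimate of a true 0.27 SD interaction therefore overstates it, unless it has the wrong sign.

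**The case against.** The strongest reply is that this is exploratory by its own heading, leaves the primary test's alpha untouched, and promises no confirmatory moderator claim. ERQ11 speaks of a prognostic model, so the 0.1 level can be read as ordinary lenient variable selection, for which a familywise error rate is not the natural yardstick. Much of this stands, and it is why the point is minor. It does not rescue the rule. Interactions with allocation are expressly included, the output feeds ERQ11, and p-value selection inflates what is kept and makes omissions uninformative whatever the label.

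A second reply is that the authors know about low power. The Sub-group analyses section says so and sends ethnicity, age, sex and severity to a separate latent-class analysis. That also stands: this model is not the only route to differential effects.

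Some stronger readings are tempting but unsupported:
- A reader might infer that the logic model will be revised on this result alone. ERQ11 makes revision conditional, and Exploring Adaptation says that the logic model also draws on qualitative, adherence, dosage, fidelity and mediator evidence.
- A reader might infer that a dropped factor will be reported as showing no difference in effect. The protocol does not say this; the risk lies in the rule's silence.
- A reader might take the interactions to be tested one at a time. The text does not fix this, and the problem remains under joint fitting.
- A reader might think that implementation-evaluation questions 9 and 10 rest on this rule. They concern causal pathways and mediation. Exploring Adaptation relates a similar factor list to 6-month outcomes, but states neither the 0.1 level nor an allocation interaction.

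**Conclusion.** The concern holds as a minor point. If the 0.1 level is applied to the allocation interactions, at least one false one is selected in about 61% of trials without moderation under independence. The range is roughly 51–67% across the correlations and fitting methods tried, and 65% under independence if expectancy is two scores. A true 0.27 SD interaction is missed about 62% of the time at 35/65 and 59% at 50/50. These power figures assume a binary factor and the protocol's own n and correlation; ethnicity in more than two categories would do no better. The rule therefore performs poorly in both directions, and its result may inform a revision of the logic model. The primary analysis is not affected.

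**What to change.** Delete the p<0.1 selection rule. In its place:
- Fit one pre-specified fractional model that keeps all listed factors and all their allocation interactions, together with the primary-model adjustment terms (site, severity, baseline substance use, pilot/efficacy indicator). Say whether expectancy is one score or two.
- Report every interaction estimate with its 95% CI, and state how many were examined.
- Label them hypothesis-generating, and state that a non-significant interaction does not show equal effect.

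Do not instead make logic-model revision conditional on a Holm adjustment at 5%. Its first step for nine tests is 0.05 / 9 = 0.0056 (z = 2.77), which leaves power of about Φ(1.34 − 2.77) ≈ 8% for a 0.27 SD interaction and so worsens the problem of missed moderators.

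The cost is wording only, on the same data and model family. With one parameter per factor the model has 1 + 1 + 9 + 9 = 20 parameters, plus site, baseline use and the pilot/efficacy indicator = 23 (severity is already among the nine). Splitting expectancy adds two, and a multi-category ethnicity variable adds more. The downside is a larger model with somewhat wider intervals, and fewer factors labelled as moderators.

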In adolescent populations a standard TLFB with a recall period of 28 days. Frequency of use is calculated as percent days abstinent from alcohol and/ or other substances in the previous 28-days. It provides a fractional outcome and is far more detailed than standard measures of alcohol and substance use and can yield information on the overall frequency of alcohol and substance use, frequency of individual substances, quantity of use and periods of heavy episodic use. With a trained researcher the TLFB28 takes on average 10 minutes to complete.

The covariate for the primary outcome is assessed at eligibility and baseline using a Single Substance Use Question (SSUQ; (Levy et al., 2021)) over the past 28-days. This single frequency question reduces the burden on participants at baseline and addresses the issue of potential assessment reactivity, where the assessment of substance use in detail acts as a brief intervention. The SSUQ meets the criterion as a covariate for adolescent populations in that it is highly correlated with frequency of substance use derived from the primary outcome time line follow-back 28 (rho = 0.903 for alcohol and 0.830 for drugs).

Secondary outcomes

Self-reported violent offending will be assessed using the volume score of the Self-Report Delinquency Scale (SRDS; (Smith and McVie, 2003)) over the previous six months. This 19-item questionnaire has established psychometric properties (Fonagy et al., 2018) in this population and has a strong correlation (R=0.95) with police charges (McAra and McVie, 2007). Violent offences are classified as carrying a weapon, robbery, assault, racial assault and fire setting.

Emotional symptoms and behavioural difficulties will be assessed using the self-completed Strength and Difficulties questionnaire (SDQ; (Goodman, 1997)). This assesses behaviour across several domains including, conduct, hyperactivity, emotional regulation, peer relationships and prosocial behaviour and allows for the generation of two multi-component outcomes: internalising and externalising behaviours with the latter highly associated with current or future offending behaviour. We will assess total score, externalising behaviour, internalising behaviour. The outcome is widely used and has demonstrated excellent validity and moderate reliability in adolescent populations (Goodman, 2001). The SDQ is suitable for

completion by those aged 10-17 years and those with mild learning disabilities (Law and Wolpert, 2014).

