We will explore the relationship between alcohol and substance use and violent offending (**PRQ5**) by comparison of data derived from the TLFB for specific substances and the SRDS. This will enable decisions to be taken about whether specific substances should be the target of the efficacy trial. Data redundancy (**PRQ6**) will be explored by examining the pattern of missing data for each outcome.

We will explore business as usual (PRQ7) through interviews with key stakeholders across both sites, those that deliver business as usual and those that refer to their services. We will explore key questions around acceptability of the intervention, factors that facilitate or hinder participation, intervention delivery and outcome assessment (PRQ8, PRQ9) by conducting interviews with young people and parents/ carers, purposively sampling those who did not consent and those who consented but dropped out of the intervention or follow up. To explore how the intervention is sensitive to the sociocultural needs of the target population and determine potential culturally influenced barriers towards the acceptability of the intervention in relation to ethnicity and equity, as well as the presence of structural barriers, we will conduct in-depth qualitative interviews with young people from minority ethnic communities and other marginalised groups including those with SEND and LAC, as well as with staff, and providers. Thematic analysis (Braun and Clarke, 2006) will be used to elicit young people's experiences of the programme, in addition to staff, and service providers' perspectives, and how these experiences impact on the acceptability of the intervention. The findings will inform future adaptations of the intervention to various socio-cultural contexts.

Efficacy study analysis

The primary analysis will take the form of a fractional regression model, adjusted for baseline stratification variables and the baseline covariate.

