An aspect of our qualitative work with key stakeholders involves examining participants' positive and negative experiences of the referral process and intervention, exploring how these perspectives concur with those who deliver the intervention, explore at what points negative and positive experiences are at their greatest and what steps could be taken to ameliorate these experiences to improve the delivery and acceptability of the intervention.

Exploring Adaptation

The mechanism of change will be explored using a latent class mediation model. Exploring factors that impact on the mechanism of change will be assess the relationship between prerandomisation factors and observed outcomes at 6 months. Pre-randomisation factors include sex, age, ethnicity, IMD decile, family cohesion, motivation to change, self-efficacy and substance use expectancy.

In addition to quantitatively understanding the mechanism of action, the qualitative analysis will provide an opportunity to explore the perceptions of the intervention from the point of view of a variety of stakeholders. The analysis will allow us to explore what elements of the interventions are useful and what elements are unnecessary, issues around how the interventions are planned and implemented and the perceived barriers or facilitators of implementation in usual practice.

Through a detailed exploration of the key dimensions, we plan on stating our logic model at the start of the project, and revise this again at the end of the internal pilot stage. The logic model will incorporate the qualitative research exploring stakeholder perceptions of acceptability and usefulness, hindrances and facilitators associated with the process and intervention but will also combine quantitative analysis exploring adherence, dosage, fidelity, and mediators associated with behaviour change. This mixed methods synthesis will enable

us to understand what works, how it works, when it works and for whom it works and provide a detailed elaboration of the mechanisms and processes through which it works.

Exploring Factors Affecting Implementation

Interviews with intervention delivery partners and key stakeholders, including those delivering similar substance use services to CYP, will explore how sustainable the intervention is in its current format. What key challenges were experienced and what changes might be necessary to roll out the intervention more widely.

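### The exploratory predictor and moderator models do not name baseline substance use or site among their factors, so a factor that only tracks baseline use can pass the 0.1 selection too often

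*Protocol*

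**What the plan says.** The protocol's Exploratory analysis section fits a fractional regression to the 6-month primary outcome. It names nine candidates: "Pre-randomisation factors will include ethnicity, sex, age, IMD decile, severity of substance use, and baseline family cohesion, motivation, self-efficacy and expectancy". It adds that "Interaction terms with allocation arm will be included in the analysis" and that "a significance level of 0.1 will be used to determine which factors are to be included in the model". A second model, in the intervention arm only, reuses these factors and adds adherence, fidelity and therapeutic alliance.

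The section cites no research question, but its content matches ERQ11, which asks for a prognostic model built on baseline characteristics of the young person and family. The stated purpose of that question is "using the results to elaborate mechanisms of change and where appropriate revise the intervention logic model".

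Under Exploring Adaptation, the process evaluation relates a similar list to 6-month outcomes: "Pre-randomisation factors include sex, age, ethnicity, IMD decile, family cohesion, motivation to change, self-efficacy and substance use expectancy". That list has eight factors and omits severity.

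Elsewhere the baseline value has a fixed role. The Primary outcome section says "The covariate for the primary outcome is assessed at eligibility and baseline using a Single Substance Use Question". The Efficacy study analysis makes the primary model a "fractional regression model, adjusted for baseline stratification variables and the baseline covariate", and secondary-outcome models also carry the stratification factors and baseline covariates. The stratification factors are site (Bristol, Newport) and two-level GAIN-SS severity. Neither exploratory list names the single substance use question or site.

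**The concern.** The variable left out is the plan's own main predictor of the outcome. The Sample size calculations put the pre-post correlation of substance use frequency at 0.4 and reduce the sample size on the strength of it.

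Several listed factors could plausibly follow current use. In Appendix IV the top of the readiness ruler describes already using less, and the situational confidence scale asks about resisting drink or drugs. If baseline use is not in the model, such a factor can carry its effect and pass the 0.1 threshold without any effect of its own.

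Severity is only a partial substitute. For stratification it is dichotomised, and the GAIN-SS items score how recently problems occurred. The item on weekly or more frequent use would be met by most people who satisfy the entry rule of at least 4 occasions in 28 days.

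At stake is the reading of ERQ11. A factor retained for this reason could be written into the logic model as part of the mechanism. In the intervention-arm model the process measures are not randomised, so baseline use is an obvious possible confounder of their associations with outcome. Leaving out a covariate that explains outcome variance also costs the interaction tests some precision.

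**Working it through.** **Inputs from the protocol.** Effect 0.27 SD, power 80%, two-sided alpha 0.05, pre-post correlation 0.4, 364 followed up (182 per arm), selection at 0.1 (taken as two-sided).

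**Assumptions.**
- ρ: correlation of a candidate factor with baseline use, 0.1 to 0.4.
- s: correlation of severity with baseline use, 0 to 0.7. In the simulations severity is a median split of a variable correlated 0.3 to 0.5 with baseline use, which gives s of about 0.24 to 0.40 (multiply by 0.798).
- The single substance use question correlates 0.4 with the outcome, which is how the plan uses it.

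**The plan's own figure.** Per arm, n = 2 × (1.960 + 0.842)² × (1 − 0.4²) / 0.27² = 180.9, so 181, or 362 in total. The t-test version is 434 × 0.84 = 364.6. Both agree with the stated 364, so 0.4 is the correlation the plan relies on.

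**Retention of a factor with no effect beyond baseline use, tested alone, severity in the model.**

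Partial correlation with outcome = (0.4ρ − 0.4s × ρs) / √[(1 − (0.4s)²)(1 − (ρs)²)].

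Example, ρ = 0.3 and s = 0.3: (0.120 − 0.0108) / √(0.9856 × 0.9919) = 0.110. On the Fisher scale, 0.111 × √360 = 2.10. Chance of passing 0.1 = Φ(2.10 − 1.645), about 68%. With s = 0.7 the partial correlation is 0.065 and the chance is 34%. With s = 0 it is 74%.

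| ρ | Formula, s = 0.7 to s = 0 | Linear simulation, latent severity correlation 0.5 to 0.3 |
|---|---|---|
| 0.1 | 13-20% | 16-19% |
| 0.2 | 21-45% | 37-42% |
| 0.3 | 34-74% | 63-70% |
| 0.4 | 52-92% | 84-90% |

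A simulated fractional logit with robust standard errors gives 38-81% at ρ = 0.3. With baseline use in the model, retention returns to about 10% (8.5-14.7% across the fractional-logit settings, 600 runs each).

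**Four such factors entered jointly.** The plan lists nine factors, and related ones share the baseline signal. In the same linear set-up, per-factor retention is about 12-17% at ρ = 0.1, 23-51% at 0.3 and 30-61% at 0.4. The lower ends add a residual correlation of 0.3 among the factors; the upper ends assume none.

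**Intervention arm only, n = 182, one factor.** The Fisher-scale term shrinks by √2. Simulated retention is 23%, 39% and 59% at ρ = 0.2, 0.3 and 0.4.

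**Interaction power, two-sided 0.1.** Leaving out baseline use multiplies the standard error by √[(1 − (0.4s)²)/0.84], which is 1.091 at s = 0 and 1.047 at s = 0.7. An interaction with 80% power in the full model needs 1.645 + 0.842 = 2.486 standard errors. Without baseline use:
- s = 0: Φ(2.486/1.091 − 1.645) = 74%.
- s = 0.7: Φ(2.486/1.047 − 1.645) = 77%.

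For a 50:50 subgroup, SE = 4√(v/364), which is 0.210 at v = 1 and 0.192 at v = 0.84. Adding baseline use raises power from 60% to 67% for a 0.40 SD interaction and from 82% to 88% for 0.54 SD, if severity explains nothing. The loss is therefore about 3 to 7 points.

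**Site.** The protocol gives no site effect on the outcome, so nothing can be computed.

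**The case against.** The analysis is labelled exploratory, the wording introducing the nine factors does not close the list, and an analysis plan could add covariates. That limits the severity. It does not remove the point, because the protocol itself fixes a list and a selection rule, the adjustment clause used for the primary and secondary models is absent here, and the two exploratory lists disagree on severity.

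A factor that tracks baseline use does predict month-6 use, so in a purely predictive model keeping it is no error. If motivation or self-efficacy influences current use, adjustment also changes the question to prediction beyond current use. Both arguments stand. The concern applies to the mechanism and moderator reading that ERQ11 intends.

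The form of severity in these models is not stated. The five GAIN-SS items are scored 0 to 4, so a graded score could absorb more of the baseline signal. This too stands, and is why s is taken up to 0.7.

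A reader might infer that such factors will be selected. The protocol gives none of the correlations needed, and at 0.1 the excess over 10% is modest. A reader might also infer that the process-measure associations go wholly unadjusted. The related regression under Exploring Fidelity/ Adherence, Differentiation, and Quality does provide for covariate adjustment, but does not name the covariates.

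**Conclusion.** The point holds as a minor one. The named factors omit baseline use and site, in contrast to the primary and secondary models, and following the lists as written lets a factor with no effect beyond baseline use be retained more often than 10%. The size depends on assumed correlations and on how many related factors enter together. It ranges from slight (12-19% at ρ = 0.1) to large (30-61% jointly, 84-90% alone, at ρ = 0.4). The loss of interaction power is real but small.

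Two stronger readings are not supported. Interaction tests do not necessarily face 19% more residual variance (1/0.84 = 1.19): that assumes the other factors explain nothing, and with s = 0.7 it is about 10% (0.9216/0.84 = 1.10). Nor is any specific harm from omitting site shown; adding it is for consistency with the primary and secondary models. The primary estimate and the progression criteria are unaffected.

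**What to change.** In Exploratory analysis (both the two-arm and the intervention-arm model) and in Exploring Adaptation, state that baseline percent days abstinent from the single substance use question, site, GAIN-SS severity and, in two-arm models, arm are forced into every model and exempt from the 0.1 selection. Apply that selection only to the remaining factors and their interactions with arm. State that the covariates in the fidelity and adherence regression include the same baseline terms.

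The cost is a few fixed terms in exploratory models, all from data already collected. Retained factors must then be reported as predictors beyond baseline use. If plain prediction is also wanted, a version without baseline use can be shown alongside and labelled as such.
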